## **Data Management**

---

*Roles responsible for management, including data collection, entry, cleaning, etc. and basic procedures and safeguards to be used.*

6.3 All data collected for analysis will be de-identified and assigned a unique study number. Data collection forms will be kept in a locked file cabinet in the office of the PI at Hebrew SeniorLife. Data will be entered and stored on a password-protected secure server at Hebrew SeniorLife.

The Institute for Aging Research primarily employs the REDCap system to facilitate data management operations. REDCap is a full-featured clinical trials data management system (DMS) accessible to data entry and data analysis workstations using secure Web technologies. The REDCap product is developed and maintained by Vanderbilt University in cooperation with REDCap Consortium members, including Hebrew SeniorLife. HSL hosts and maintains a dedicated instance of REDCap for use across our research enterprise. Each research study is provided separate project workspace in which all of the study data are stored in a MySQL relational database on the private corporate network behind several firewalls and located physically within the HSL data center.

## **7.0 Foreseeable Risks, Potential Benefits, Compensation and Costs to Participants**

---

### **Potential medical risks of study procedures**

---

TESTS OF WALKING AND PHYSICAL FUNCTION: The proposed walking tests have been adapted from the large-scale, population-based MOBILIZE Boston study (PI: [name]) and multiple completed and ongoing clinical studies within the Clinical Research Laboratory at IFAR. They have been designed to be safe for individuals of varying risk and conditioning levels including older adult fallers. The physical activity associated with these tests is of low to moderate intensity. Potential risks include strains, sprains, muscle soreness, and light-headedness. In rare instances, more serious side effects such as an injurious fall may

occur. For all functional tests, a trained "spotter" will stand behind or close to the subject to provide stabilizing assistance if necessary. Subjects will be instructed to stop performing or skip any test that makes them feel uncomfortable. Adequate rest will be given in between each test, and any reusable equipment will be cleaned with disinfectant after each use.

**MAGNETIC RESONANCE IMAGING (MRI) :** Participants will be asked to participate in one brain MRI. They will rest in a horizontal position on the imaging table that slides into a magnetic field. All studies performed under this protocol will not exceed the FDA guidelines for magnetic resonance in any way. Therefore, the risks assumed by the participant are the same as in any noninvasive protocol involving whole body MRI. The presence of metal objects could cause a burn injury, but by following strict MRI exclusion guidelines, this risk will be minimized. Participants may feel claustrophobic or anxious during the procedure and they may experience musculoskeletal or back discomfort lying on the scanner table. The MRI makes loud banging noises as it takes images. Under some circumstances nerve stimulation may occur, which may be experienced as a mild twitching reaction in limbs and/or lower back muscles. Such effects are rare and scan settings are kept well below the levels where such effects are known to occur. MR imaging also requires the use of radio waves that can cause a mild warming similar to exposure to hot weather. Body temperature may increase but by less than two degrees Fahrenheit. Participants will be instructed to inform MRI personnel should they experience discomfort due to warming and the procedure will be stopped.

## 7.1

**TRANSCRANIAL DIRECT CURRENT STIMULATION (tDCS):** tDCS has been widely used during the last decade demonstrating non-significant risk to participants. Expected side effects include:

1) Sensations reported by subjects under the electrodes: (These sensations can sometimes continue throughout and for a brief period following completion of the tDCS but usually resolve shortly after the initiation of tDCS)

- Mild tingling (20-70%)
- Light itching (30-40%)
- Slight burning (10-22%)
- Discomfort or mild pain (10-18%)

2) Other effects that can occur both during and after tDCS include:

- Mild fatigue (15%)
- Skin redness (20%)
- Headache (10-15%)
- Difficulties in concentration (11%)

3) Additionally the following rare side effects have been described:

- Nausea (<(<1%)

- Nervousness (<1%)
- Although it has never been reported in tDCS, seizures are a theoretical risk. Individuals with a history of seizures and/or a diagnosis of epilepsy will therefore be excluded from this study.

## **Potential psychosocial (non-medical) risks, discomforts, inconveniences of study procedures**

---

TESTS OF MENTAL FUNCTION: Risks associated with answering these cognitive test questions are minimal, but participants may experience mental fatigue and/or anxiety during this form of testing.

INCONVENIENCES: We will minimize the risk to subjects in this study by excluding those with conditions listed in the exclusion criteria. The proposed protocol requires multiple visits and therefore considerable participant burden with respect to time and effort. Our study team has a strong track record of successful clinical research requiring similar participation, and retention has been high in these projects. The Clinical Research Laboratory at IFAR is located next to a cafeteria and equipped with comfortable seating, a TV, movies, books and magazines to keep individuals occupied during resting periods. Several additional strategies will be employed to minimize participant burden and maximize adherence to the protocol. We will:

7.2

- Develop a personal relationship between participants and members of the staff by matching research assistants with individual participants.
- Schedule appointments at convenient times with familiar staff.
- Explain to participants all aspects of their participation and follow up. We will demonstrate and practice study procedures before beginning data collection.
- Provide reminders of all appointments and follow-up phone calls.
- Include personal notes in the participant's data file to remember events in the life of the participant; these can be commented on at the next visit (e.g., birthday, birth of a grandchild).
- Provide snacks during all visits.
- Provide transportation for all visits, if required
- Provide valet or dedicated, on-site parking spaces.
- Compensate participants for visits.

## **Potential benefits to individual participants as a result of participating the study**

---

Participants may not receive any significant health benefit from participation, although some may benefit from knowledge of their health status, as well as potential therapeutic effects of tDCS.

7.3

Participants will be provided an up to \$460 stipend to help cover the costs of their time spent completing study procedures and visits. We believe that the potential benefits of establishing tDCS as a noninvasive intervention to improve executive function and mitigate the risk of future cognitive decline in older adults outweigh the potential risks, which are expected to be minor, transient and relatively rare.

### **Potential benefits to study population, community, or society**

---

7.4

The observations from these studies are expected to provide important information regarding the effects of noninvasive electrical brain stimulation on both physical and cognitive function in older adults who have recently fallen due to poor balance, and who are fearful of falling again in the future. Results are also expected to provide insights into the feasibility and effectiveness of a tDCS intervention within this population, thus increasing the potential for deployment of tDCS interventions to larger numbers of older adults.

### **Describe any provisions for medical care and available compensation in the event of injury**

---

7.5

Any subject who suffers an adverse event during the conduct of study protocols at Hebrew SeniorLife will be given immediate medical care at the Hebrew SeniorLife by the medical investigators, and, if the event meets the definition of a serious adverse event, the participant will be removed from the study, and will be referred to their primary care physician for ongoing care. The treating provider will bill the insurance company or other third parties, if appropriate, for the care a participant receives for any injury. We will try to have these costs paid for, but the participant may be responsible for some of them. For example, they may be responsible for payment of any deductibles and co-payments required by the insurer. There are no plans to provide any compensation for an injury beyond what is described above, should one occur.

If the event does not meet the criteria of a serious adverse event, and the participant is willing and able to continue, he/she will be able to continue and complete the study.

### **Will there be remuneration for participants?**

7.6

---

*e.g. goods, services, gift cards, cash, etc.*

Yes

### **Describe the type remuneration and the timing of remuneration to study procedures**

---

*e.g. participants will be provided with \$50 per study visit, to be distributed as visits are completed, etc..*

Participants will receive the following stipends after completing each activity:

- Visit 1: In-person screening and study familiarization - \$30
- Visit 2: MRI study at the BIDMC - \$50, plus transportation and/or parking reimbursement
- Visit 3: Baseline assessment visit - \$45
- Visits 4 - 23: tDCS intervention visits (Twenty visits @ \$10 each, will be completed Mon-Fri over four consecutive weeks = \$200)
- Visits 24-26: Follow up assessments (repeat of baseline visit) immediately post-intervention; at 3 months post intervention, and at six months post intervention. \$45 each x 3 = \$135

This is total of \$460 for participants who complete the entire study.

Participants will be offered snacks at all study visits. Transportation will be provided for all study visits, if needed.

**No**

**Will participants incur any costs due to participating in the study?**

7.7

*e.g. transportation, parking, etc.*

**Yes**

**No**

## **8.0 Safety Assessment and Study Monitoring**

**Definitions of adverse event and serious adverse event for the study**

An adverse event is any untoward medical occurrence in a participant, whether or not is is causally related to the study. An adverse event can therefore be any unfavorable and unintended sign (including an abnormal laboratory finding, for example), symptom or disease temporally associated with the study. Adverse events will be recorded on the appropriate case report forms and source documents. The investigator and/or trained staff member will evaluate all adverse events as to their severity and relation to the test article. The

severity of adverse events will be graded as follows:

8.1

- Mild: Awareness of a sign or symptom but easily tolerated.
- Moderate: Discomfort sufficient to cause interference with usual activity or to affect clinical status.
- Severe: Incapacitating with inability to do usual activity or to significantly affect clinical status.
- Life Threatening: The participant was at immediate risk of death from the adverse event as it occurred.

The Investigator will also assess the relationship of any adverse event to study, based upon available information, using the following guidelines:

- 0 = Unlikely: No temporal association, or the cause of the event has been identified.
- 1 = Possible: Temporal association, but other etiologies are likely to be the cause; however, involvement of the study procedures cannot be excluded.
- 2 = Probable: Temporal association, other etiologies are possible, but not likely.

A serious adverse event is any experience that results in any of the following outcomes: death, is life threatening, inpatient hospitalization or prolongation of hospitalization, a persistent or significant disability/incapacity. Important medical events that may not result in death, be life-threatening, or require hospitalization may be considered a serious adverse event when, based upon appropriate medical judgment, they may jeopardize the patient or participant and may require medical or surgical intervention to prevent one of the outcomes listed in this definition.

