### **Unanticipated problem and adverse event reporting**

---

*Include the method, distribution and time frame (e.g. to IRB, to DSMB, etc.*

8.2

Unanticipated problems and adverse events will be reported according to the Hebrew SeniorLife's IRB written guidelines for interventional studies. Serious adverse events will be reported to the Hebrew SeniorLife's IRB within 24hrs by fax or email, with a written report submitted within 5 business days of learning of the event, and submission of the incident via the eIRB system within one week of learning of the event. This form will record any adverse symptoms and/or study protocol deviations.

All adverse events/study incidents will be reported to the HSL IRB, according to policy, within 5 business days of learning of the event, and to submit the incident via the eIRB system within one week of learning of the event.

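### Adverse-event relatedness grade 0 (Unlikely) takes in any event whose cause is known, device-caused events included, and no grade describes an established device cause

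*Combined protocol and SAP*

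**What the plan says.** The scale stands in section 8.1 (Definitions of adverse event and serious adverse event for the study) and has three grades. The lowest is worded "0 = Unlikely: No temporal association, or the cause of the event has been identified". The middle grade, Possible, is for an event whose timing fits and for which another cause is the likelier one, although the study procedures cannot be ruled out. The highest is worded "2 = Probable: Temporal association, other etiologies are possible, but not likely", and no grade follows it.

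The section introduces the assessment twice. After the definition of an adverse event it says "The investigator and/or trained staff member will evaluate all adverse events as to their severity and relation to the test article". After the severity grades it says "The Investigator will also assess the relationship of any adverse event to study, based upon available information, using the following guidelines". No other section defines relatedness, qualifies grade 0 or gives a second scale.

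**The concern.** A relatedness scale should move an event up as the evidence for the device or procedure grows. Here the second limb of grade 0 depends only on whether a cause is known, not on which cause it is. An event with a firmly established device cause therefore satisfies the definition of the lowest grade, while one with a merely suspected device cause can reach the highest. The top grade leaves room for doubt, so it does not describe an established relation either. In addition, with two targets named, the reader of a coded record cannot tell whether the grade refers to stimulation or to something else in the study, such as a walking test.

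What is at stake is the attribution recorded for each event, and any safety summary built on it. Section 8.1 lets either an investigator or a trained staff member judge relation to the test article. Consistency between raters then rests on the written definitions.

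**Working it through.** No arithmetic applies. The check is to apply the three definitions, as worded, to test events. The inputs are the grades in section 8.1 and the risks listed in section 7.1 (Potential medical risks of study procedures).

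**Event A: a skin reaction under an electrode, right after a session, with stimulation established as the cause.**

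| Grade | What it requires | Met by event A? |
|---|---|---|
| 0 Unlikely | no temporal association, *or* cause identified | Yes: the first limb fails, the second is satisfied, and either one is enough |
| 1 Possible | temporal association, with other causes likely | No: no other cause is likely |
| 2 Probable | temporal association, with other causes possible but not likely | Nearest in sense, but not strictly: no other cause is in play |

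**Event B: an illness traced to a source unrelated to the trial.** The cause is identified, so grade 0 applies, as intended. Events A and B thus receive the same code, although their relation to the device is opposite.

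**Comparison within the scale.** Grades 1 and 2 both speak of *other* etiologies. Grade 0 speaks only of the cause. The restricting word is missing in the one place where it decides the code.

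**Event C: a sprain probably caused by a walking test.** Section 7.1 lists sprains among the risks of the physical tests and lists stimulation effects separately. Judged against the test article, event C belongs low on the scale. Judged against the study, it is Probable. The two introductory sentences support different targets, and grade 1 itself refers to study procedures. One could read them as asking for two assessments, since the second says that the investigator will *also* assess. On that reading only relation to the study has defined grades, and relation to the test article has none. On either reading, the device's own contribution is not separately graded.

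**Does anything else in the plan depend on the grade?**

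- Reporting to the IRB (section 8.2) covers all adverse events.
- Reporting to the DSMB (section 8.3) covers all incidents, after review of each event.
- Removal of a participant turns on seriousness (section 7.5), or on the participant's request or the type of event (section 8.3).
- The statistical plan (section 6.0) contains no analysis of related events.

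None of these uses the grade.

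**The case against.** The strongest answer is that nobody would apply grade 0 this way. The clause defines the label Unlikely on a scale of relationship to the study, so the identified cause is naturally a non-study cause. The references to other etiologies in grades 1 and 2 point the same way. The section calls the grades guidelines, to be used with the available information. An investigator facing an obvious electrode injury would choose Probable, the highest grade on offer. On this view the lack of a definite grade costs only the distinction between probable and definite, which the plan never uses.

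Much of this stands. The intended meaning is very probably an alternative cause, and the wording is no evidence of intended miscoding. The practical safeguards are also real. Section 8.2 says "All adverse events/study incidents will be reported to the HSL IRB, according to policy, within 5 business days of learning of the event", whatever the grade. Section 5.1 has participants complete a side-effects questionnaire at the end of each visit, so expected local effects are captured apart from the relatedness code. All-event rates can be compared between the randomised arms without any attribution. Events C and A might also be told apart by their description on case report forms, which are not part of the text available here.

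What does not stand is the inference that the wording is adequate. The rater must set aside a satisfied definition to reach the sensible code, and must then use a grade that still allows for other causes. A better description on the form would separate a walking injury from a stimulation injury, but would not say which target the grade refers to.

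**Conclusion.** The point holds as a wording defect of limited reach. Followed literally, section 8.1 codes an event known to be caused by the device as Unlikely, offers no grade that fits an established relation, and leaves the target of the assessment unclear. The effect is confined to the recorded attribution of adverse events and any safety summary that relies on it.

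Two stronger readings are tempting, and the documents support neither.

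- A reader might infer that a comparison between arms of tDCS-related events will be unreliable. Section 6.0 plans no such comparison.
- A reader might multiply the side-effect rates in section 7.1 by the arm size and take the result as a number of miscoded events. Those rates describe expected sensations and redness; the slight burning listed there is a sensation under the electrode, not a burn injury. The documents do not say how many such effects would be recorded as adverse events, or how raters would grade them.

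The conclusion rests on two assumptions. The first is that no rater instruction outside these documents already corrects grade 0. The second is that neither the IRB's written guidelines, cited in section 8.2, nor the DSMB charter, which section 8.4 describes as still to be developed, makes an action depend on the grade. If either did, the defect would matter more.

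**What to change.** Make three changes in section 8.1 and on the adverse-event form:

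1. Reword grade 0 as *no temporal association, or a cause other than stimulation or study procedures has been identified*.
2. Widen the top grade to include events with no other plausible cause, or add a grade above it for them.
3. State whether relation is to stimulation or to study procedures. Two separate items would be better than one, so that an injury in a walking test and a stimulation effect are not recorded under one attribution.

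The cost is wording and at most one extra form field, with slightly more coding per event. No visit, sample size or efficacy analysis changes. It is best done before events are coded, because later regrading would rest on retrospective judgement.

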### **Unanticipated problem and adverse event reporting**

---

*Include the method, distribution and time frame (e.g. to IRB, to DSMB, etc.*

8.2

Unanticipated problems and adverse events will be reported according to the Hebrew SeniorLife's IRB written guidelines for interventional studies. Serious adverse events will be reported to the Hebrew SeniorLife's IRB within 24hrs by fax or email, with a written report submitted within 5 business days of learning of the event, and submission of the incident via the eIRB system within one week of learning of the event. This form will record any adverse symptoms and/or study protocol deviations.

All adverse events/study incidents will be reported to the HSL IRB, according to policy, within 5 business days of learning of the event, and to submit the incident via the eIRB system within one week of learning of the event.

### **Process for data and safety monitoring**

---

Only those listed on the approved IRB protocol will have access to subject data. Subject data will be coded and locked in a file cabinet in a locked office. Identifying information will not be used during discussion, presentation or research publication. The criteria for discontinuing

8.3 a participant's participation include the participant's request, as well as any unexpected life-threatening or potentially disabling event, including syncope, an injurious non-accidental fall, hemodynamic collapse, stroke, transient ischemic attack, dysrhythmia, renal insufficiency, angina, myocardial infarction, anaphylaxis, acute hemorrhage, or hospitalization for acute illness. Any adverse events that take place during testing will be reported by the PI ([name]) to [name], Director of Institute for Aging Research, Professor of Medicine at HMS and Chief of Gerontology at BIDMC and recorded in the database. [name] will have primary responsibility for monitoring participant safety in the trial. The investigators will be responsible for reviewing each adverse event in a timely fashion, and reporting all incidents to the DSMB in accordance with the established DSMB charter, and preparing a summary report. Any adverse events will be reported to the Hebrew SeniorLife IRB according to written guidelines.

8.4 **Will there be a data safety monitoring board (DSMB) or committee reviewing the research?**

---

Yes

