#### **Withdrawal of participants**

---

*Include any anticipated circumstances when participants will be withdrawn without their consent, how participants will be withdrawn, including use of any collected data and follow-up with any new/pertinent information.*

4.7

If during the course of their study enrollment, a participant develops a new medical condition that would make participation in the study contraindicated, as determined by a study physician ([name]), the participant will be informed of this and withdrawn from the study. All data collected prior to withdrawal will be maintained in the study data set.

**4.8 Will you be enrolling participants who may have diminished capacity to provide informed consent or to understand study procedures (now or in the foreseeable future)?**

---

Yes

No

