Intervention characteristics: Each intervention will comprise 20, 20-minute sessions of stimulation completed over four consecutive weeks. Our pilot RCT demonstrated significant effects of 10 tDCS sessions over two weeks in a similar population of older adults over a shorter follow-up period. At the same time, several well-designed trials have recently reported lasting benefits of multi-session tDCS interventions on depression, pain, stroke, and Parkinson's disease, which have each tested interventions ranging from 8-20 sessions. We therefore believe 20 sessions constitutes a safe and feasible intervention, and that it will maximize the duration of expected effects, yet not over-burden participants with study visits. tDCS sessions will be administered at approximately the same time of day. Participants will continue taking their medications throughout the intervention, and will be asked to inform the study team of a change in medication usage.

Double-blinding and safety procedures: tDCS will be delivered by personnel certified in tDCS administration by the Berenson-Allen Center for Noninvasive Brain Stimulation at the BIDMC, which is directed by our co-investigator, [name]. Similar to our most recent studies, tDCS will be delivered using the Startstim-8™ device and software (Neuroelectrics Corp, Cambridge MA), which enables custom amounts of current to be delivered through an array of eight Pi™ gel Ag/AgCl electrodes placed on the scalp according to the 10-20 EEG convention. Study personnel administering tDCS and the participants will not be aware of tDCS intervention arm assignment. We will ensure such double-blinding by programming the tDCS software with intervention-specific stimulation codes, as supplied by personnel uninvolved in data collection, prior to study initiation. At the end of each visit, subjects will complete a questionnaire to report potential side effects (e.g., skin irritation, headache, etc). In accordance with recent recommendations, the efficacy of tDCS blinding will also be assessed by asking each participant—and study team member administering tDCS—to judge whether real or sham tDCS was given, as well as their certainty of this judgment. This questionnaire will be completed at the end of the first tDCS session, at the end of the last tDCS session and at the final follow-up assessment.

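### Rules that end participation after serious or contraindicating events make no provision for follow-up once stimulation is stopped or already complete

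*Combined protocol and SAP*

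**What the plan says.** Three places end participation:

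- **Section 8.3, Process for data and safety monitoring.** The criteria for discontinuing "a participant's participation include the participant's request, as well as any unexpected life-threatening or potentially disabling event". The list continues "including syncope, an injurious non-accidental fall, hemodynamic collapse, stroke, transient ischemic attack" and closes with "acute hemorrhage, or hospitalization for acute illness". It states no location or study period and does not mention stimulation.
- **Section 7.5, provisions for medical care.** For adverse events during study procedures at the site, "if the event meets the definition of a serious adverse event, the participant will be removed from the study".
- **Section 4.7, Withdrawal of participants.** A participant who "develops a new medical condition that would make participation in the study contraindicated", as determined by a study physician, is withdrawn. On data, the section says only this: "All data collected prior to withdrawal will be maintained in the study data set".

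The surrounding design:

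- **Stimulation (section 5.1).** "Each intervention will comprise 20, 20-minute sessions of stimulation completed over four consecutive weeks".
- **Follow-up (sections 5.1 and 3.1).** Visits 24-26 fall within three days of the last session and at three and six months. Section 3.1 ties falls tracking to the length of study participation. Section 5.1 explains that falls are tracked because resulting injuries may affect physical and cognitive performance.
- **Analysis (section 6.0).** Participants are included by randomised arm, and missing records are multiply imputed. Arm differences are estimated at each time point to judge how long effects last. The named sensitivity analyses concern sex, age, BMI and other covariates.

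**The concern.** The three rules treat leaving the intervention and leaving the study as one act. For most of the time at risk there is no stimulation left to stop, so applying the rule then ends only observation. The triggering events are of a kind that can themselves change the outcomes, so data would be lost for reasons related to the values that go unseen.

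The imputation would draw on what was recorded before removal and on participants who stayed. It would have nothing on the course after the event. If that course is worse than imputed, and removal differs between arms, the 3- and 6-month contrasts shift, and those contrasts carry the duration-of-effect question. SPPB (Aim 2) is the clearest case. Dual task cost is less certain: it is a percent change from single to dual task, and an injury may slow both conditions.

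**Working it through.** **1. The plan's own figures reproduce.**

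- Aim 1 (SD 20, correlation 0.75, 57 per arm, difference 8): adjusted SD = 20 × √(1 − 0.75²) = 13.23. Power = Φ(8 / (13.23 × √(2/57)) − 1.96) = 0.898, against the stated 90%.
- Aim 2 (SD 1.5, correlation 0.75, 57 per arm, difference 0.5): the SE of the three-visit average, adjusted for baseline, is 1.5 × √((1 + 2 × 0.75)/3 − 0.75²) × √(2/57) = 1.5 × √(0.833 − 0.5625) × 0.187 = 0.146. Power is 0.928, against the stated 92%.

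**2. Data lost per removed participant.** Assume events spread evenly over 4 + 26 = 30 weeks, with the three-month visit at week 17.

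- Share of events before Visit 24: 4/30 = 0.133
- Share before Visit 25: 17/30 = 0.567
- Share before Visit 26: 1
- Expected visits lost: 0.133 + 0.567 + 1 = 1.70 of 3
- Expected calendar weeks lost: 30/2 = 15 of 30

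**3. Data lost in total.** The documents give no event rates, so 2-5% removal is assumed. That is 144 × 0.02 = 2.9 to 144 × 0.05 = 7.2 people, or 4.9 to 12.2 of 144 × 3 = 432 planned assessments (1.1-2.8%).

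**4. Possible shift in SPPB at 6 months.** Shift = arm difference in removal × amount by which the unseen value lies below the imputed one. The arm difference is assumed at 2 to 5 points and the shortfall at 0.5 to 1.5 units. The SE at 6 months alone is 1.5 × √(1 − 0.75²) × √(2/57) = 0.186.

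| Arm difference | Shortfall | Shift (units) | Shift / SE | False-positive rate |
|---|---|---|---|---|
| 0.02 | 0.5 | 0.010 | 0.05 | 5.0% |
| 0.05 | 0.5 | 0.025 | 0.13 | 5.2% |
| 0.02 | 1.5 | 0.030 | 0.16 | 5.3% |
| 0.05 | 1.5 | 0.075 | 0.40 | 6.9% |

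The last column is Φ(−1.96 + z) + Φ(−1.96 − z), with z = shift / SE.

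These arm differences are large relative to the assumed removal. Two points at 2% overall means 3% against 1%, and five points at 5% overall means 7.5% against 2.5%. Both are threefold imbalances.

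**5. Shift on the three-visit average.** Fewer participants are missing at the earlier visits, so the 6-month shift is multiplied by 1.70/3 = 0.567. The range becomes 0.006 to 0.043 units. At the top, z = 0.043/0.146 = 0.29, and the false-positive rate is about 6.0%.

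**6. Effect of the fix.** If half of those removed could still be tested, the 6-month shift halves to 0.005-0.0375 units.

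**The case against.** - **No sentence forbids later data collection.** This stands. A reader might infer that the protocol bars follow-up of removed participants. The documents do not go that far: section 8.3 lists criteria without making removal mandatory, and section 4.7 leaves the decision to a physician. Loss of follow-up is the plain reading of the wording, and no supplied text says otherwise.
- **The fall trigger is narrow.** A reader might infer that any injurious fall ends participation in a trial of recurrent fallers. Section 8.3 limits it to unexpected, life-threatening or potentially disabling events and to falls described as non-accidental, a term it does not define. Tracking falls because injuries affect performance also presumes that many injured participants stay and are tested. This limits the number removed.
- **Many qualifying events would prevent testing anyway.** Previous stroke, recent myocardial infarction and recent hospitalization for acute illness are entry exclusions, and the outcomes require repeated 60-second standing and walking trials. The gain from continued follow-up is therefore partial.
- **Bias needs removal to differ by arm.** If tDCS has no effect on such events, systematic removal is equal. If tDCS prevents injurious falls, more decliners leave the sham arm and the bias runs against tDCS. A spurious benefit would need tDCS to cause disabling events. The pilot reported no adverse events in 20 participants, and the side effects listed in section 7.1 are mostly mild. This makes the upper rows of the table unlikely.
- **Attrition is already budgeted.** The plan allows 15% attrition and 20% total missingness, and power at that level reproduces. A reader might infer a power shortfall; the figures do not show one. The budget covers how many are missing, not why.
- **Sections 7.5 and 8.3 may seem to conflict** over a non-serious syncope or fall on site. Section 7.5 keeps only those willing and able to continue, and section 8.1 adds that "Important medical events that may not result in death, be life-threatening, or require hospitalization may be considered a serious adverse event". Together these largely reconcile the two, so I make no point of it.

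**Conclusion.** The gap is real but probably small. For participants removed under sections 4.7, 7.5 or 8.3, the supplied text makes no provision for later assessments or calendars. The plan then relies on imputation without post-event data and names no analysis that tests this.

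Size and direction are unknown. Under the assumed rates and imbalance, the bias reaches at most 15% of the 0.5-unit SPPB target at 6 months (0.075/0.5) and about 9% on the three-visit average (0.043/0.5). The upper shortfall of 1.5 units is a full baseline SD and has no support in the documents. The false-positive rates further require no true SPPB effect together with arm-related removal. This is a cheap improvement, not a flaw that threatens the main result. It is best settled in advance, because follow-up that is not collected cannot be recovered at analysis.

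**What to change.** Use the same rule in sections 4.7, 7.5 and 8.3, for example: *Participants who meet these criteria stop stimulation. Visits 24-26 and falls calendars continue for everyone who still consents and whom the study physician judges safe to test.* Define a non-accidental fall at the same time.

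Add to section 6.0 one delta-adjusted sensitivity analysis for those still missing after such an event. For SPPB, set their values 0.5 to 1.5 units below the imputed value, varied by arm.

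The cost is protocol and consent wording plus one analysis. The visits and calendars are already planned. Some visits will need rescheduling after an event, and a physician must confirm that testing is safe. The proposal takes no position on which events should stop stimulation.
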